**Doses for neutropenic fever or nadir cytopenias:**

ADVERSE EVENTS	REDUCTION OF DOSE FOR SUBSEQUENT CYCLES
Febrile neutropenia or Grade 4 neutropenia	1 st occurrence: reduce irinotecan to 75% of previous dose and delete the bolus 5FU dose  2 nd occurrence: reduce oxaliplatin to 75% of previous dose  3 rd occurrence: treatment discontinuation
Grade 4 thrombocytopenia	1 st occurrence: reduce oxaliplatin and 5FU (bolus and infusion) to 75% of previous dose  2 nd occurrence: reduce irinotecan and 5FU (bolus and infusion) to 75% of previous dose  3 rd occurrence: treatment discontinuation

### 7.3.2 Diarrhea

Patients must be instructed in the use of loperamide for diarrhea, and must have a supply of this drug upon starting FOLFIRINOX. Patients should not be retreated with irinotecan until recovery from diarrhea to  $\leq$  grade1 (without loperamide for at least 24 h) has occurred. Diarrhea is attributed to chemotherapy UNLESS a specific infectious agent is isolated.

ADVERSE EVENTS	REDUCTION OF DOSE FOR SUBSEQUENT CYCLES
Diarrhea grade 3-4 or Diarrhea + fever and/or neutropenia grade 3-4	1 st occurrence: reduce irinotecan to 75% of previous dose and delete bolus 5FU dose  2 nd occurrence: reduce oxaliplatin and continuous infusion 5FU to 75% of previous doses  3 rd occurrence: treatment discontinuation
Diarrhea <math>\geq</math> 48 h despite high doses of loperamide	Hold FOLFIRINOX until resolves to $\leq$ grade1 for at least 24 hrs.  No dose reductions after complete recovery, unless gr 3-4 diarrhea, or diarrhea + fever and/or concomitant neutropenia gr 3-4

### 7.3.3 Mucositis or Hand-Foot Syndrome

Grade  $\geq$  2: Hold treatment until toxicity resolves to a  $\leq$  grade 1, then resume oxaliplatin, irinotecan, and leucovorin at 100% of the previous dose and fluorouracil (bolus + infusional 5-FU) at 75% of the previous dose for all subsequent doses. For subsequent grade  $\geq$  2 recurrence(s), hold treatment until toxicity resolves to a  $\leq$  grade 1, then resume oxaliplatin, irinotecan, and leucovorin at 100% of the previous dose and fluorouracil (bolus + infusional 5-FU) at 75% of the previous dose.

### 7.3.4 Cardiac Toxicity

For any cardiac arterial thrombotic event or ischemic event (angina, myocardial infarction) discontinue all protocol therapy.

### 7.3.5 Increased Bilirubin

In case of elevation of bilirubin, evaluation to exclude biliary obstruction or progressive disease is recommended. For bilirubin  $>1.5x$  ULN, omit irinotecan until bilirubin is  $<1.5x$  ULN.

### 7.3.6 Neurotoxicity

#### Toxicity Scale for the Sensory Neuropathies Associated with Oxaliplatin

	Symptoms
Grade 1	Paresthesias/dysesthesias* of short duration that resolve and do not interfere with function
Grade 2	Paresthesias/dysesthesias* interfering with function, but not with activities of daily living (ADL)
Grade 3	Paresthesias/dysesthesias* with pain or with functional impairment that also interfere with ADL.
Grade 4	Persistent paresthesias/dysesthesias* that are disabling or life threatening.
	* May be cold-induced

- For grade 2 neurotoxicity persisting between treatments: Reduce oxaliplatin to 75% of the previous dose for all subsequent cycles.
- For grade 3 neurotoxicity resolving to  $\leq$  grade 2 between treatments: Reduce oxaliplatin to 75% of the previous dose for all subsequent cycles.
- For grade 3 neurotoxicity persisting between treatments: Discontinue Oxaliplatin. Patients should continue to receive other protocol therapy.
- For grade 4 neurotoxicity: Discontinue oxaliplatin. Patients should continue to receive other protocol therapy.

### 7.3.7 Other Toxicities

For  $\geq$  grade 2 toxicity attributed to treatment and not described above (except fatigue, anemia and alopecia), hold treatment until toxicity resolves to  $\leq$  grade 1 and resume treatment with the agent that is thought to be causing the toxicity at 75% of the previous dose and all other agents at full dose.

If grade 3-4 toxicity is clearly secondary to a single agent and is thought to be cumulative, the causative agent may be discontinued with the approval of the principal investigator. Similarly, a causative agent may be discontinued for grade 2 allergic reaction and must be discontinued for grade 3-4 allergic reaction.

### 7.3.8 Extravasation

Extravasation of oxaliplatin is reported to cause necrosis. Extravasation should be treated according to institutional guidelines.

### 7.3.9 Dose Modification for Obese Patients

There is no clearly documented adverse impact of treatment of obese patients when dosing is performed according to actual body weight. Therefore, all dosing is to be determined solely by the patient's BSA as calculated from actual weight.

## 7.4 Concomitant Medications

### 7.4.1 Anti-emetics:

Due to the emetogenic nature of this regimen, Emend will be administered with each cycle in addition to concomitant antiemetics at the discretion of the treating physician.

For symptoms of nausea and vomiting during radiation, anti-emetics (such as ondansetron or prochlorperazine) will be given one hour prior to SBRT, and as needed following SBRT.

### 7.4.2 Loperamide:

For symptoms of diarrhea and/or abdominal cramping that occur at any time during a treatment cycle or during radiation, patients will be instructed to begin taking loperamide. Loperamide should be started at the earliest sign of (1) a poorly formed or loose stool or (2) the occurrence of 1 to 2 more bowel movements than usual in 1 day or (3) an increase in stool volume or liquidity. Loperamide should be taken in the following manner: 4 mg at the first onset of diarrhea, then 2 mg every 2 hours around the clock until diarrhea-free for at least 12 hours. Patients may take loperamide 4 mg every 4 hours during the night. The maximum daily dose of loperamide is 16 mg/day.

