### 6.1 Neoadjuvant mFOLFIRINOX

Patients will receive eight cycles of neoadjuvant mFOLFIRINOX – one cycle every two weeks (+/- 3 days). One cycle is defined as 14 days, and treatment will be initiated on day one of a two week cycle. The drugs will be dosed and administered as follows:

- Oxaliplatin  $85 \text{ mg/m}^2$  IV infused over two hours, followed by
- Leucovorin  $400 \text{ mg/m}^2$  IV (or levoleucovorin  $200 \text{ mg/m}^2$  IV) over two hours
- Irinotecan  $135 \text{ mg/m}^2$  IV over 90 minutes (concurrent with leucovorin during the last 90 min of the leucovorin infusion)
- 5-FU  $300\text{mg/m}^2$  IV bolus, then  $2400 \text{ mg/m}^2$  continuous IV infusion over 46 hours

All patients will receive supportive care as follows:

- Pegfilgrastim (NeulastaTM) on day 3, 4, or 5.

- Anti-emetics including palonosetron or ondansetron, aprepitant, and dexamethasone, according to standard institutional protocols.
- Atropine is administered per standard guidelines for cholinergic symptoms during irinotecan infusion on day 1.
- Loperamide is administered per standard guidelines for chemotherapy-induced diarrhea.
- Patients will be counseled regarding potential side effects and their management.

Re-staging pancreas protocol CT scans will be performed after 3 and 7 cycles of mFOLFIRINOX. MRI can be substituted for patients unable to undergo a CT scan. A PET scan is optional if necessary for re-staging.

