### 7.4.4 Antibiotics:

Oral fluoroquinolone treatment may be initiated for ANC<500 or diarrhea for >24 hours despite loperamide, at the discretion of the treating physician.

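### The loperamide schedule in section 7.4.2 exceeds its own 16 mg daily maximum in longer episodes, and no section says what to do when the maximum is reached

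*Combined protocol and SAP*

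**What the plan says.** Section 7.4.2 applies to diarrhea or cramping during a chemotherapy cycle or during radiation. It sets a low threshold for starting: "Loperamide should be started at the earliest sign of (1) a poorly formed or loose stool" is the first of three triggers. The regimen is "4 mg at the first onset of diarrhea, then 2 mg every 2 hours around the clock until diarrhea-free for at least 12 hours". An alternative follows: "Patients may take loperamide 4 mg every 4 hours during the night". The paragraph ends with the limit: "The maximum daily dose of loperamide is 16 mg/day". It does not say which instruction prevails.

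Other sections foresee longer episodes. Section 7.4.4 allows an oral fluoroquinolone, at the physician's discretion, for "diarrhea for >24 hours despite loperamide". The table in section 7.3.2 holds FOLFIRINOX when diarrhea has lasted at least "48 h despite high doses of loperamide".

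On patient education, section 7.3.2 says "Patients must be instructed in the use of loperamide for diarrhea" and requires patients to have a supply when chemotherapy starts. Section 6.1 adds "Patients will be counseled regarding potential side effects and their management" and refers loperamide use to standard guidelines, without giving a dose.

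**The concern.** A fixed two-hourly schedule with a stop rule of 12 symptom-free hours sits beside a daily ceiling that it overruns within the first day. Patients dose themselves, starting at the first loose stool, so the written rule has to work without a clinician present. A patient who keeps to the schedule goes 8 to 10 mg a day over the protocol's own limit. A patient who keeps to the limit runs out of permitted doses while diarrhea may be continuing, and is told nothing about what comes next. Section 7.2.4 warns that severe diarrhea on irinotecan can be fatal and that late diarrhea needs prompt loperamide, so neither outcome should be left to guesswork. What is at stake is a safety instruction, not the trial's inference.

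**Working it through.** **Inputs, all from section 7.4.2.** First dose 4 mg at hour 0; then 2 mg every 2 h; stop after 12 h free of diarrhea; night option 4 mg every 4 h; maximum 16 mg/day.

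**Conventions.** The dose falling exactly at 12 diarrhea-free hours is not required. Calendar-day results use start times on even clock hours. Where the limit is applied, dosing resumes as soon as it allows.

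**Schedule as written.**
- Cumulative dose at hour h (even) = 4 + 2 × (h/2) mg: 14 mg at hour 10, 16 mg at hour 12, 18 mg at hour 14.
- First 24 h: 12 doses, 4 + 11 × 2 = 26 mg, which is 10 mg over the limit.
- Each later full day: 12 × 2 = 24 mg, which is 8 mg over.
- Night option: 4 mg / 4 h = 1 mg/h, the same as 2 mg / 2 h. An 8-hour night on this option still gives 26 mg on the first day and 24 mg on a later day.

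**Which episodes fit.** With symptoms lasting L hours, doses fall at hours 0, 2, … up to but not including L + 12. The course total is 4 + 2 × ((L + 12)/2 − 1) mg.

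| Symptoms (h) | Course total (mg) | Largest calendar-day total over start times (mg) |
|---|---|---|
| 0 | 14 | 8 to 14 |
| 2 | 16 | 8 to 16 |
| 4 | 18 | 10 to 18 |
| 12 | 26 | 14 to 26 |
| 24 | 38 | 20 to 26 |

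Up to 2 h of symptoms always fits. From 4 to 12 h it depends on the start time and on how a day is counted. At 24 h, every start time exceeds 16 mg on at least one calendar day.

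**If the maximum governs, counted over any 24 h.**
- Day 1: doses at hours 0 to 12 give 4 + 6 × 2 = 16 mg. The 5 doses at hours 14 to 22 are lost, leaving 24 − 12 = 12 h between doses.
- Day 2: doses at hours 24 to 38 give 8 × 2 = 16 mg. The 4 doses at hours 40 to 46 are lost, leaving 48 − 38 = 10 h between doses.
- 24 h of diarrhea: 18 scheduled doses (hours 0 to 34), 4 + 17 × 2 = 38 mg. Permitted: 7 + 6 = 13 doses, 28 mg. Lost: 5 of 18.
- 48 h of diarrhea: 30 scheduled doses (hours 0 to 58), 4 + 29 × 2 = 62 mg. Permitted: 7 + 8 + 6 = 21 doses, 44 mg. Lost: 9 of 30.

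**If the maximum governs, counted by calendar day.**

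| Period | Doses lost, by start time | Amount taken (mg) |
|---|---|---|
| First 24 h of dosing | 0 to 5 of 12 | 16 to 26 |
| 24 h of diarrhea | 3 to 5 of 18 | 28 to 32 |
| 48 h of diarrhea | 7 to 9 of 30 | 44 to 48 |

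In the first 24 h nothing is lost for starts from 10:00 to 16:00, because midnight resets the count; such a patient takes the full 26 mg in 24 h without breaching a calendar-day limit. Five doses are lost only for a midnight start.

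**Steps elsewhere.** The fluoroquinolone option (more than 24 h) and the chemotherapy hold (at least 48 h) depend on how long diarrhea lasts. Neither is tied to reaching 16 mg, which on the any-24-h count happens at hour 12.

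**The case against.** The best reply is that a ceiling is a limiter and not a contradiction. Dosing at an interval up to a daily maximum is a common form, the maximum comes last in the paragraph, and it has no exceptions. On that reading there is one rule: dose every two hours and stop at 16 mg. This largely stands, and it rules out the stronger inference that the paragraph cannot be obeyed at all. It does not rescue the instruction to keep dosing through the day and night until 12 symptom-free hours have passed, and it supplies no step at the limit.

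A reader might also infer that every patient with a day of diarrhea loses 5 of the first 12 doses and waits 12 hours. The documents do not support that. The text says per day, not per any 24 hours, and by calendar day the first-24-hour loss runs from 0 to 5 doses.

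Nor do the documents show that patients would be misdosed in practice, or that diarrhea management is missing. Instruction and counseling are required, section 6.1 refers to standard guidelines, section 7.2.4 calls for careful monitoring and prompt treatment, and two duration-based steps exist. The patient instructions themselves are not in the documents and may already settle the matter. These safeguards reduce the gap, but none states what to do at 16 mg.

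**Conclusion.** The point holds as an inconsistency within section 7.4.2 that no other section resolves. The excess over the stated maximum, 10 mg in the first 24 hours and 8 mg on each later full day, is exact arithmetic. Short episodes are unaffected; the conflict is certain for the longer ones that sections 7.4.4 and 7.3.2 expect. The number of doses lost if the maximum governs rests on how a day is counted, so the ranges should be quoted and not the extreme alone. That the maximum governs is the natural reading, but the documents do not show which instruction was intended. The finding concerns the protocol text only. It is a minor patient-safety correction, worth making because patients treat themselves, and it does not touch the primary endpoint, the sample size or the error rates.

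**What to change.** Amend section 7.4.2 in three respects:
- State that the 16 mg maximum overrides the dosing schedule, including the night option.
- Define whether the limit applies to a calendar day or to any 24 hours. Any 24 hours is the cautious choice, but it would narrow the present wording, so the sponsor should adopt it knowingly.
- Give a step for a patient who reaches the limit with continuing diarrhea, for example to stop loperamide and call the clinic. The clinical choice is the sponsor's to confirm.

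Then check that the patient instructions say the same. The cost is a sentence or two of protocol text and that check. Design and analysis do not change.

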### 7.4.3 Proton Pump Inhibitors (PPIs):

All patients will be prescribed proton pump inhibitors to start at least by the first SBRT treatment, and to continue for a minimum of 6 months after completion of SBRT, or at least until surgery for those undergoing resection.

### 7.4.4 Antibiotics:

Oral fluoroquinolone treatment may be initiated for ANC<500 or diarrhea for >24 hours despite loperamide, at the discretion of the treating physician.

### 7.4.5 Anticoagulants:

Prophylactic or therapeutic doses of Coumadin or low-molecular weight heparin are permitted.

### 7.4.6 Low-dose aspirin ( $\leq$ 325 mg/d):

Aspirin may be continued if the patient was on this prior to enrollment.

### 7.4.7 Growth Factors:

Pegfilgrastim (Neulasta) will be administered with each cycle of therapy but can be omitted after the first cycle at the discretion of the treating physician for hyper-leukocytosis on day 1 of treatment.

## 8. REQUIRED CLINICAL AND LABORATORY EVALUATIONS

To be completed within 14 days (2 weeks) before the first dose of study drug:

- All blood work, History, Physical Examination, and Performance Status

To be completed within 21 days (3 weeks) before the first dose of study drug:

- Imaging studies (CT or MRI, and PET scans)

To be completed within 42 days (6 weeks) before the first dose of study drug:

- Endoscopic Ultrasound (EUS)

CT with pancreatic protocol will be obtained at the following time points: (1) at baseline, (2) after cycle 3 of chemotherapy, (3) after cycle 7 of chemotherapy within 4 weeks prior to SBRT, and (4) pre-operatively within 4 weeks prior to surgery. For patients who cannot undergo CT, MRI is allowed.

### Calendar of Assessments

Neoadjuvant mFOLFIRINOX:					
Tests & Observations	Screening			Day 1 of each cycle	Day 3, 4, or 5 of each cycle
	Within 14 days of starting study drug	Within 21 days of starting study drug	Within 42 days of starting study drug		
Scheduling Window (Days)				(±3)	(±3)
Surgical Evaluation			x		
History & Physical	x			x	
Height	x				
Weight/BSA	x			x	
Vital Signs	x			x	
Performance Status	x			x	
Toxicity Assessment	x			x	
Neulasta Q					x
Laboratory StudiesA:					
CBC, Diff, Platelets	x			x	
Serum Chemistries B	x			x	
PT/INR C	x				
CA 19-9, CEA	x				
Pregnancy Test D	x				
Research Blood Collection E	x				
Staging:					
CT (or MRI) F		x			
EUS (with elastography) G			x		
Neulasta					x
Tissue:					
Core Biopsy H			x		

Neoadjuvant SBRT and Pre-Operative Evaluation:			
Tests & Observations	Pre-SBRT (within 4 weeks prior to RT)	Weekly During SBRT	Pre-operative (within 4 weeks prior to surgery)
Surgical evaluation			x
History & Physical	x	x	
Weight/BSA	x	x	
Vital Signs	x	x	
Performance Status	x	x	
Toxicity Assessment		x	
Laboratory Studies:			
CBC, Diff, Platelets	x		x
Serum Chemistries B	x		x
PT/INR C			x
CA 19-9, CEA	x		x
Research Blood Collection E	x I	x J	x K
Staging:			
CT (or MRI) F	x		x K
EUS (fiducials and elastography) G	x		x L
Tissue:			
Core Biopsy H	x		

Adjuvant mFOLFIRINOX and Post-Treatment Follow-Up:					
Tests & Observations	Day 1 of 1 st adjuvant cycle (within 12 weeks of surgery)	Day 3, 4, or 5 of each cycle	Day 1 of each subsequent cycle	Post-Treatment Follow-Up N	30-day follow-up
Scheduling Window (Days)	(±3)	(±3)	(±3)	(± 14)	(± 7)
History	X		X	X	X
Physical Exam	X		X	X	X
Weight/BSA	X		X	X	X
Vital Signs	X		X		
Performance Status	X		X	X	
Toxicity Assessment	X		X		
Neulasta Q		X			
Laboratory StudiesA:					
CBC, Diff, Platelets	X		X	X	
Serum Chemistries B	X		X	X	
CA 19-9, CEA	X			X	
Research Blood Collection E	X			X O	
Staging:					
CT (or MRI) F				X P	X
Tissue:					
Surgical Resection M					

Long Term Follow-up PeriodN:			
Tests & Observations	Every 3 months (for the first three years after completing mFOLFIRINOX)	Every 6 months (three years after completing mFOLFIRINOX for the next two years)	Annual (five years after completing mFOLFIRINOX)
Scheduling Window (Days)	Every 3 months ±14 days	Every 6 months ±14 days	Annually ± 14 days
History	x	x	x
Physical Exam	x	x	x
Weight/BSA	x	x	x
Performance Status	x	x	x
Laboratory StudiesA:			
CBC, Diff, Platelets	x	x	x
Serum Chemistries B	x	x	x
CA 19-9, CEA	x	x	x
Research Blood Collection E	x	x	x

Follow-up PeriodN:		
Staging:	Every 6 months (first three years after completing mFOLFIRINOX)	Annually (three years after completing mFOLFIRINOX for two years)
Scheduling Window (Days)	Every 6 months ±14 days	Annually ±14 days
CT (or MRI) F	x	x

- A** Laboratory studies must be drawn within 24 hours of administration of drugs
- B** Serum chemistry panel will include serum creatinine, BUN, electrolytes (Na, K, Cl, Bicarb), AST/ALT, Alk Phos, Bili, and albumin
- C** PT/INR should be monitored weekly for those taking coumadin or warfarin
- D** For women of child-bearing potential only
- E** 3 purple top tubes (30 mls) at diagnosis, and 2 – 3 purple top tubes (20 – 30 mls) at each follow up time point, for cryopreservation of plasma and buffy coat
- F** CT should be performed using pancreatic protocol when possible. For patients who are unable to undergo CT, MRI may be used
- G** If elastography is not feasible, patients can remain on study
- H** At the time of diagnosis, core biopsies will be attempted with one specimen sent to pathology for diagnosis and a separate specimen to be banked for correlative studies. If core biopsies are not successful, a FNA is acceptable for diagnosis. At the time of EUS for fiducial placement, a core biopsy will be obtained and banked for correlative studies. Patients can continue on study if core biopsy is not feasible at the time of fiducial placement.
- I** At the time of CT simulation
- J** On the day of fraction 3 and fraction 5 of SBRT
- K** CT scan and plasma and serum samples will be done within 4 weeks prior to surgery
- L** Endoscopic ultrasound is optional if deemed necessary for surgical assessment

- M** Tissue from the surgical specimen will be banked for correlative studies
- N** Initiated within 4 weeks of completing all treatment and continued every 3 months for three years, then every six months for two years, then annually or until disease recurrence or death
- O** At completion of 12 cycles of FOLFIRINOX, at follow up every 3 months for 3 years, then every 6 months for 2 years, then annually until recurrence or death, and at the time of disease progression
- P** Initiated within 4 weeks of completing all treatment, then every 6 months for three years, and then annually for 2 years or until disease recurrence
- Q** Administered with each cycle of therapy but can be omitted after the first cycle at the discretion of the treating physician for hyper-leukocytosis on day 1 of treatment.

## 9. CRITERIA FOR RESPONSE AND PROGRESSION

Response to treatment will be assessed by the treating physicians and investigators according to RECIST version 1.1, as follows:

### 9.1 Definitions

#### 9.1.1 Measurable Disease:

*Tumor lesions:* Must be accurately measured in at least one dimension (longest diameter in the plane of measurement is to be recorded) with a minimum size of:

- 10 mm by CT scan (CT scan slice thickness no greater than 5 mm).
- 10 mm caliper measurement by clinical exam (lesions which cannot be accurately measured with calipers should be recorded as non-measurable).
- 20 mm by chest X-ray.

*Malignant lymph nodes:* To be considered pathologically enlarged and measurable, a lymph node must be  $\geq 15$  mm in short axis when assessed by CT scan (CT scan slice thickness recommended to be no greater than 5 mm). At baseline and in follow-up, only the short axis will be measured and followed.

#### 9.1.2 Non-Measurable Disease:

All other lesions, including small lesions (longest diameter  $<10$  mm or pathological lymph nodes with  $\geq 10$  to  $<15$  mm short axis) as well as truly non-measurable lesions. Lesions considered truly non-measurable include: leptomeningeal disease, ascites, pleural or pericardial effusion, inflammatory breast disease, lymphangitic involvement of skin or lung, abdominal masses/abdominal organomegaly identified by physical exam that is not measurable by reproducible imaging techniques.

### 9.2 Methods of Measurement

The same method of assessment and the same technique should be used to characterize each identified and reported lesion at baseline and during follow-up. Imaging based evaluation should always be done rather than clinical examination unless the lesion(s) being followed cannot be imaged but are assessable by clinical exam.

Computed tomography (CT) / MRI - CT and MRI might be the best currently available and reproducible methods to measure target lesions selected for response assessment. Conventional CT and MRI should

be performed with cuts of 5 mm or less in slice thickness contiguously. Spiral CT should be performed using a 5-mm contiguous reconstruction algorithm.

